8.0 RESEARCH QUESTION AND OBJECTIVES

The objective of the Menveo Pregnancy Registry is to evaluate pregnancy outcomes among women immunized with the Menveo vaccine within 28 days prior to conception or at any time during pregnancy. The primary outcomes of interest include major congenital malformations (MCM), preterm birth, and low birth weight (LBW).

Other pregnancy outcomes will be collected, including stillbirths and SABs. The probability of SAB varies greatly as a function of when the pregnancy is enrolled in the registry ([Savitz, 2002](#)). Because pregnancies will be reported to the registry at different and imprecise times during gestation, calculation of the prevalence rate of SAB from the registry is deemed inappropriate and could lead to erroneous conclusions. For example, if a woman enrolls in the registry at 16 weeks of pregnancy, only an SAB after this time could be detected and included in prospective reports. Similarly, SABs occurring earlier in gestation may not have been recognized and/or reported.

This registry is primarily descriptive and designed to detect potential safety signals rather than test hypotheses.

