NVD did not study vaccination in pregnancy as one of the objectives of clinical studies before licensure. Pregnant women were excluded from enrollment, and the use of birth control, where appropriate, was an entry criterion. Despite this requirement, 43 women in studies V59P13, V59P17, and V59P18 were found to be pregnant during the 6-month follow-up period. Of these women, 37 were administered MenACWY. All 7 spontaneous abortions occurred among women vaccinated with MenACWY.

In addition to reports in clinical trials, NVD received reports of 10 additional instances of MenACWY exposure during pregnancy via passive post marketing safety surveillance. One pregnancy ended in spontaneous abortion (SAB) 52 days after vaccination with both MenACWY and a rabies vaccine. Two pregnancies ended in normal deliveries of healthy infants, and the outcomes of the remaining 7 pregnancies are unknown.

The Menveo Pregnancy Registry is established to meet a CBER post marketing commitment (PMC) and is designed to collect prospective data on pregnancy outcomes among women immunized with the Menveo vaccine within 28 days prior to conception or

at any time during pregnancy. The 28-day window prior to conception was established based on data from the Menveo product label (Menveo package insert, 2012). Effectiveness of the Menveo vaccine in subjects 11 through 55 years of age was evaluated in a randomized, controlled clinical study comparing the hSBA responses following 1 dose of Menveo, showing that 68%-75% subjects have seroresponse 28 days after vaccination with Menveo.

Menveo is not indicated in pregnancy. However, inadvertent pregnancy exposures are anticipated because the targeted age group for the vaccine includes young women of reproductive potential. The registry will add to the current clinical experience with Menveo by supplementing data from animal toxicology studies and human exposure data. Pregnancy data will be collected at registry enrollment, at the end of the second trimester of pregnancy, and at pregnancy outcome for both mother and infant. NVD sponsors the registry in consultation with specialists from appropriate fields such as obstetrics, pediatrics, clinical research, genetics, epidemiology, and teratology from academic institutions, private practice, and/or government agencies. These individuals constitute the Scientific Advisory Committee (SAC) and will provide an independent review of registry data.

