9.5 Study Size

Currently the market share of Menveo is approximately 20%, with an annual absolute dose distribution of 1.8 million in 2012. It can be assumed that market shares will remain stable over the course of the 3-year duration of the study. The Advisory Committee on Immunization Practices (ACIP) recommends routine administration of a MenACWY vaccine for all persons aged 11 through 18 years. A single dose of vaccine should be administered at age 11 or 12 years, and a booster dose should be administered at age 16 years. It is roughly estimated that of all Menveo vaccinations, approximately 76% are provided to individuals less than 18 years of age ([Novartis Vaccines and Diagnostics, 2012](#)). Given the low rate of pregnancy in this age group, exposure during pregnancy at the recommended ages can be expected to occur infrequently. Likewise, vaccination among women of peak reproductive age (25-29 years) can also be expected to be rare ([Ventura, 2012](#)). In addition, willingness to participate and completion of follow-up in the pregnant adolescent population are expected to be very low. It is therefore anticipated that, per year, approximately 15 exposed women will be enrolled through the registry system and that approximately 60 supplemental identified exposures of Menveo in pregnancy can be expected from external sources.

The registry is expected to prospectively enroll approximately 100 women with exposure to Menveo 28 days prior to conception or during pregnancy over a 3-year period. Approximately 58% of these pregnancies can be expected to result in a live birth ([Ventura, 2012](#)). Given the patient population will be mainly adolescents, a high percentage of these pregnancies can be expected to be unintended, unwanted, and likely

to result in IAB. Therefore, it is anticipated that the registry will yield approximately 58 live births. It is expected that the vast majority (99%) of pregnancy exposures will occur within 28 days prior to conception or early in the first trimester (before pregnancy status is known). If exposures occur later in pregnancy, results will be stratified by trimester of exposure, acknowledging that the power of stratified analyses to detect statistically significant differences will be limited by the sample size of each subgroup.

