Invalid registry reports and pregnancies deemed lost to follow-up will be excluded from the primary analysis. Retrospective reports will not be included, although retrospective cases with MCMs will be reviewed and reported separately for signal detection purposes.

Sequential Pregnancies

The number and outcome of sequential pregnancies will be noted and presented. Sequential pregnancies will be included in the analytic dataset.

Multiple Gestation Pregnancies

The number, type (e.g., twin, triplet), and outcome of multiple gestation pregnancies will be noted and presented. Multiple gestation pregnancies will be included in the analytic dataset.

General Considerations for Data Analyses

This study is observational, and epidemiological methods will be employed for data collection and analyses.

Descriptive analysis will be performed for all prospective, evaluable data. The summary statistics for continuous and categorical variables to be used will be specified in the statistical analysis plan (SAP) but may include means, standard deviations, medians, minimums, maximums, percentiles, n's, and percentages. Adjustment for confounders of potential associations will be made with multivariate regression methods if appropriate and will be described in detail in the SAP.

The registry will identify the number of cases for the primary outcomes of MCM, preterm birth, LBW, and in addition for second trimester SABs; proportions of these outcomes will be calculated with 1-sided 95% confidence intervals from the total number of pregnant women or live births, or in the case of second trimester SABs, the subset of women exposed prior to the 20th week of gestation.

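### Section 8.0 rules out any SAB rate, yet 9.7 plans a second-trimester SAB proportion with the same entry-time bias, and no entry-adjusted estimate covers earlier losses

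*Protocol*

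**What the plan says.** - **Section 8.0** names major congenital malformation, preterm birth and low birth weight as primary outcomes. Of SAB it says that "calculation of the prevalence rate of SAB from the registry is deemed inappropriate and could lead to erroneous conclusions". It gives two reasons: reports arrive at varying and imprecise gestational times, and early losses may go unrecognised or unreported. Its example is a woman who enrols at 16 weeks. No gestational limit is attached to the bar.
- **Section 9.7** (General Considerations) lists the primary outcomes "in addition for second trimester SABs" and plans proportions with 1-sided 95% confidence intervals. The second-trimester SAB denominator is the women exposed before week 20. Enrolment time is not mentioned.
- **Section 9.3.3** defines SAB as a loss before 20 weeks. **Section 9.7.3** starts the second trimester at week 14.
- **Section 7.0** reports that "43 women in studies V59P13, V59P17, and V59P18 were found to be pregnant during the 6-month follow-up period". It continues: "Of these women, 37 were administered MenACWY", and "All 7 spontaneous abortions occurred among women vaccinated with MenACWY". From post-marketing reports: "One pregnancy ended in spontaneous abortion (SAB) 52 days after vaccination with both MenACWY and a rabies vaccine". Of the rest: "Two pregnancies ended in normal deliveries of healthy infants, and the outcomes of the remaining 7 pregnancies are unknown". No other adverse human pregnancy outcome is reported.
- **Section 9.5** expects 99% of exposures "within 28 days prior to conception or early in the first trimester (before pregnancy status is known").
- SABs are actively solicited as serious adverse events (11.0). Annual updates count them beside totals enrolled, with known outcome, pending and lost (12.2). The Scientific Advisory Committee reviews the accumulated data (9.4.4).

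**The concern.** The objectives section and the analysis section give different instructions. One says that an SAB rate from this registry would mislead because women enter at different times. The other calculates such a rate for part of gestation, with a denominator that takes no account of when women entered. Moving to the second trimester does not escape the difficulty: the example in 8.0, entry at week 16, lies inside the window that 9.7 analyses.

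The reason in 8.0 is sound against a crude proportion. It does not rule out an estimate that adjusts for entry time, and none is planned. Most SAB risk is likely to fall before the second trimester, close to the expected time of exposure. Those losses will appear as counts beside enrolment totals. Such counts depend on how early women happened to enrol, so they are hard to set against any literature rate.

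**Working it through.** The protocol states no size or power figure for SAB, so there is none to reproduce. Its 80% power figures for the three primary outcomes do reproduce (exact binomial, n = 58, 1-sided 5%): 80.1%, 79.9% and 79.8%.

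**1. The Section 7 counts.** Of 43 trial pregnancies, 37 were in MenACWY recipients, so 43 − 37 = 6 were not.
- MenACWY: 7/37 = 18.9%, exact 95% CI 8.0% to 35.2%.
- Not MenACWY: 0/6, exact 95% CI 0% to 45.9%.
- Chance that all 7 fall among the 37: C(37,7)/C(43,7) = 0.32 one-sided. Fisher's two-sided p = 0.57.
- The documents give no background SAB rate. For assumed rates of 10%, 12%, 15%, 20% and 25%, P(7 or more of 37) is 0.07, 0.15, 0.32, 0.63 and 0.85.

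The counts neither show nor exclude an excess.

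**2. Crude proportion against delayed entry.** These inputs are assumptions: SAB risk of 15% over weeks 5 to 19, weekly hazard falling in proportion to exp(−0.25 × week), 100 women, uniform entry, no induced abortions and no loss to follow-up.
- Crude proportion = mean over entry weeks e of 1 − Π(1 − h_t) for t ≥ e.
- Delayed-entry estimate = 1 − Π(1 − d_t/n_t), where n_t counts women enrolled by week t and still pregnant.

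| Entry weeks | Crude proportion, mean | Delayed entry, mean | Delayed entry, 95% sampling range |
|---|---|---|---|
| 5–7 | 12.0% | 15.0% | 7% to 24% |
| 5–13 | 6.7% | 15.0% | 4% to 31% |
| 5–19 | 4.4% | 15.5% | 2% to 37% |

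The crude figure changes almost threefold with entry time alone. Delayed entry removes nearly all of that bias, at a heavy cost in precision when entry is late.

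**3. The second-trimester proportion in 9.7.** Under the same assumed hazard, about 92% of SAB risk falls before week 14. A woman enrolled and pregnant at week 14 has a remaining risk of r = 1.35%. The planned denominator also includes women who lost the pregnancy before week 14, women who entered part-way through the window, and women who entered at week 20 or later, who cannot contribute an SAB by definition. If a fraction c enters at week 20 or later and all others are at risk from week 14, the planned proportion is r × (1 − c):
- c = 0.25: 1.35% × 0.75 = 1.0%
- c = 0.50: 1.35% × 0.50 = 0.7%

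The other two groups push it lower still. In 100 women this concerns about one event.

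**4. Are the data there?** Yes. Registration date is a minimum enrolment criterion (9.2.3). EDD or corrected EDD, outcome date and gestational age at outcome are collected (9.4). One definition needs settling: 9.4.1 counts week 14 from conception or LMP, origins about two weeks apart.

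**5. Sources.** Section 9.5 expects about 15 registry enrolments a year and about 60 exposures from external sources. If the 60 is annual, external sources supply 60/75 = 80%. If it is a three-year total, they supply 60/(3 × 15 + 60) = 60/105 = 57%. The external sources are not named in 9.5, but 9.7 treats networks and HMOs as reporting every exposed pregnancy. Where that holds, late voluntary entry is less of an obstacle.

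**The case against.** **The registry does follow SAB.** This stands. SABs of any gestation are solicited, counted with enrolment and known-outcome totals, listed with gestational ages and reviewed. A reader might infer that the registry cannot assess SAB, or that its counts have no denominator. The documents do not support either reading; what is missing is time at risk. One safeguard is narrower than it looks: retrospective fetal losses are reviewed, but 9.7 keeps retrospective reports out of the database unless a congenital anomaly is reported.

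**There is no demonstrated signal.** This stands too. A reader might infer from Section 7 that MenACWY raises SAB risk. The comparison gives p = 0.57, the timing of conception relative to vaccination is not stated, the post-marketing case also received rabies vaccine, and 7 of the 10 post-marketing outcomes are unknown.

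**Delayed entry does not cure everything.** Correct. Unrecognised losses remain unseen and imprecise dates remain imprecise. With only 58% live births expected and many induced abortions (9.5), a plain Kaplan–Meier curve would also be inadequate. When the assumed true risk was raised from 15% to 29%, with entry over weeks 6 to 20, fewer than half of simulated registries exceeded the 95th percentile expected without an excess.

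**This is SAP detail.** Only partly. The estimator could be left to the SAP, but the bar is in the objectives and the conflicting proportion is in the protocol's analysis section. An SAP could not reconcile them without departing from one.

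**Conclusion.** The point holds as a conflict between 8.0 and 9.7, together with a missing entry-adjusted estimate. That conflict, and the absence of any enrolment condition in the 9.7 denominator, are read directly from the text and rest on no assumption. The size of the bias does rest on an assumed hazard and entry pattern: a crude figure of 4.4% to 12.0% where the true risk is 15%, and a second-trimester risk of 1.35% diluted to about 0.7% to 1.0% if a quarter to a half of women enter at week 20 or later.

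The case for an estimate is that SAB is the only adverse human outcome in the background data and that nearly all exposures are expected around conception or early in the first trimester. A reader might go further and expect the estimate to settle whether SAB is raised. It would not, given sampling ranges as wide as 2% to 37% before induced abortions and loss to follow-up are allowed for. This is a worthwhile correction to a descriptive registry and does not undermine its primary outcomes.

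**What to change.** 1. **Section 8.0.** Replace the bar with wording such as: No crude SAB proportion will be reported. Cumulative SAB risk to 20 weeks among prospectively enrolled, recognised pregnancies will be estimated descriptively, with delayed entry at gestational age at registration, with induced abortion, ectopic and molar pregnancy as competing events (cumulative incidence), and with a 95% CI.
2. **Section 9.7.** Replace the second-trimester proportion with the same left-truncated estimate, conditional on being enrolled and at risk from the start of the second trimester. State one time origin for week 14, here and in 9.4.1.
3. **Network and HMO reports.** Show complete-capture sources separately. Start risk time no earlier than the later of pregnancy recognition and vaccination, because earlier time would count weeks in which a loss could go unrecorded.
4. **Reporting.** State with the result that the interval is expected to be very wide, that unrecognised early losses are not observed, and that the estimate cannot confirm or dismiss an excess.

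The cost is protocol and SAP wording plus one additional analysis. The dates for enrolled women are already collected. For network reports, the date of pregnancy recognition must be available or approximated by a stated rule.

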9.0 RESEARCH METHODS

9.1 Study Design

The Menveo Pregnancy Registry is a prospective, observational study of pregnant women immunized with the Menveo vaccine within 28 days prior to conception or at any time during pregnancy. It is strictly observational; the schedule of office visits and all treatment regimens will be determined by the treating health care provider (HCP). The registry will collect data that are routinely documented in the patient's medical record in the course of usual care.

The design of this pregnancy registry follows current Food and Drug Administration (FDA) guidance for designing and implementing pregnancy exposure registries ([FDA, 2002](#)).

9.2 Setting

9.2.1 Study Period

The pregnancy registry will be implemented after approval by applicable regulatory authority and central institutional review board (IRB). The target enrollment goal of the registry is 100 prospectively enrolled pregnant women. The data collection process for each participant will begin at enrollment (during pregnancy), and follow-up will occur at the end of the second trimester (approximately 24 weeks' gestation) and at pregnancy outcome (delivery or early termination).

9.2.2 Study Subjects

The study population will include pregnant women within the US who were immunized with the Menveo vaccine within 28 days prior to conception or at any time during pregnancy. Because the vaccine is not indicated in pregnancy, the majority of exposures will likely be inadvertently administered in the first trimester of pregnancy. Enrollment and data collection will be coordinated through a registry coordination center (RCC). Eligible pregnant women may self-enroll in this pregnancy registry, and HCPs may also report de-identified data on pregnancy exposures and outcomes.

9.2.3 Study Population Selection

The minimum criteria required for enrollment into the registry are as follows:

- Sufficient evidence to confirm that Menveo exposure occurred within 28 days prior to conception or at any time during pregnancy

- Sufficient information to determine whether the pregnancy is prospectively or retrospectively registered (ie, whether the outcome of pregnancy was known at the time of first contact with the registry)
- Date the pregnancy exposure is registered
- Full reporter (ie, HCP) contact information to allow for follow-up (name, address, etc.)

Because registry enrollment is open to all eligible pregnant women, an active recruitment campaign will reach out to immunization providers and their patients in a broad variety of settings. The recruitment strategy will target HCPs who are known to immunize patients specifically with the Menvo vaccine. These providers will be identified through NVD Menvo distribution data and medical science liaisons (MSLs), as well as HCP provider networks and health maintenance organizations (HMOs).

This targeted awareness will include the distribution of a comprehensive informational kit designed to solicit interest among pregnant women in registry participation. All messaging will be in line with product labeling.

The kit may include:

- Branded registry information sheet and/or brochure that will briefly describe the registry purpose and procedures
- Enrollment form and sample patient consent form
- Prescribing information
- Participant consent to contact card (this card enables the RCC to contact the potential patient and provide additional information about the registry)

Persistent awareness activities incorporating the above awareness materials as well as a variety of other approaches such as internet, product labeling, and messaging by MSLs may also be used, including the following:

- Internet:
 - FDA listing of pregnancy registries on www.fda.gov
 - www.clinicaltrials.gov
 - Society for Maternal-Fetal Medicine listing of registries
 - PPD website
 - NVD website
- Print:
 - Menvo prescribing information

- Menveo medication guide
- Medical journal advertising and/or direct to physician advertising
- Registry contact information in report(s)
- Education:
 - MSL outreach to treating HCPs
 - Scientific presentations and publications
 - Distribution of report(s) to HCPs

9.2.3.1 Reference Groups

Given the inherent difficulties in identifying a comparison group (Covington, 2009), several different methods may be used to review the data for safety signals. As described below, background rates from external surveillance sources and rates from published literature will be the primary comparators. To the extent possible, comparator rates will be age-adjusted to reflect the age distribution of the Menveo Pregnancy Registry population.

Background Rates on Pregnancy Outcomes

Background rates in the general population on pregnancy outcomes, such as premature birth and LBW, are readily available from national vital statistics or publications in the scientific literature (Martin, 2012).

Background Rates on Congenital Anomalies

Published rates of MCMs are available from the Centers for Disease Control and Prevention (CDC)'s Metropolitan Atlanta Congenital Defects Program (MACDP), which is an ongoing population-based birth defects surveillance program (Correa, 2007). The primary objectives of MACDP are to regularly and systematically monitor births of malformed infants for changes in incidence or other unusual patterns suggesting environmental influences, and to develop a case registry for use in epidemiological studies. MACDP actively searches for MCMs among the 50,000 annual births to residents of metropolitan Atlanta's 5 counties and abstracts medical records at all Atlanta obstetric hospitals, Atlanta pediatric referral hospitals, genetics labs, and vital records (Correa-Villasenor, 2003). While there are inherent problems with comparing data from women exposed to specific vaccines in pregnancy with background rates from the general population, this is not an unrealistic comparison (Honein, 1999), and background rates may be the only practical comparator. MACDP has been used as a comparator by over 60% of pregnancy registries identified in a recent survey (Covington, 2009). When an analysis includes data from an external comparator, it is important to thoroughly

understand the methodology of the external comparator, and to take this into consideration when designing the analysis plan ([Kennedy, 2004](#)).

Background Rates from Literature or Other Studies

The registry is committed to identifying other appropriate comparison groups, and research of the literature and other sources, such as other pregnancy registries or observational studies, will continue in order to obtain appropriate background rates.

